6.5.3 Adverse events

The occurrence of adverse events from visit V1 to V6 will be recorded. The frequencies of adverse events in the treatment groups between V1 and V6 will be presented in cross-tabulations; a group comparison will be made using a chi-square test if applicable.

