1 STUDY BACKGROUND

1.1 STUDY OBJECTIVES

The main research question is whether the current "Behavioral Test for the Development of medications for Alcohol Dependence" (TEMA) can demonstrate that the administration of acamprosate or ionized Calcium (Ca^{2+} = finished drug Calcium-Verla®) reduces the willingness to work for alcohol in a laboratory experiment following a 15- to 20-day period of alcohol abstinence.

The willingness to work for alcohol is determined by the cumulative number of work trials in the "constant attention task" (CAT). The change in this willingness due to the administration of acamprosate, Ca²⁺, or placebo is expressed as the difference in the cumulative number of work trials in the CAT per test day between Visit 2 (without medication) and Visit 5 (after administration of scamprosate, Ca²⁺ or placebo).

The hypothesis to be tested is that the administration of acamprosate compared to placebo or the administration of calcium ions compared to placebo, leads to a significant reduction in the willingness to work in the laboratory experiment to obtain alcohol.

Based on literature reports that form the basis of the sample size calculation, a relevant change is considered to be a reduction in blood alcohol concentration (BAC) of at least 0.1 per mille in one of the active treatment groups between Visit 2 and Visit 5 compared to the placebo group. In terms of the primary endpoint, this corresponds to a reduction in the cumulative number of work trials for alcohol infusions by 60.

Secondary objectives

The study aims to investigate whether:

- 1. the administration of acamprosate or calcium ions (Ca^{2+} = ready-to-use drug Calcium-Verla®) compared to placebo leads to altered subjective perception of alcohol effects
- 2. the efficacy of acamprosate or calcium ions can be predicted by basal levels or the change over time in measures of body calcium reserves reflecting a possible calcium deficiency
- 3. the administration of acamprosate or calcium ions reduces alcohol craving in daily life
- 4. the frequency of reported alcohol consumption during the imposed abstinence period differs between the treatment groups and how this affects the willingness to work for alcohol after the imposed abstinence period
- 5. participation in the study promotes the motivation to change drinking habits or alters drinking habits or the utilization of addiction treatment services

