1.2 STUDY DESIGN

This is a monocentric study in a placebo-controlled, randomized design with three treatment groups. The administration of the investigational drugs is conducted in a double-blind manner with placebo, acamprosate, or calcium carbonate.

The comparison will be made between the calcium group and the placebo group, as well as between the acamprosate group and the placebo group.

Self-infusion of the NIMP (alcohol / saline solution) will be conducted openly regarding the preparation and single-blind regarding the dosage during visits alcohol self-administration visits V2 and V5.

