4.3.2 Endpoints related to safety/tolerability during the treatment period

- 1. Occurrence of adverse events from visit V1 to V6 [SAESEQ]
- 2. CIWA-Ar-Score, values for blood pressure and pulse for screening and visits 1 to 6 [CIWA].

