6.3 EXPOSURE TO THERAPY AND COMPLIANCE

Randomization will be stratified according to the two criteria:

- a) Severity of addiction characteristics up to the time of V4
 - "High" if there is at least a moderate alcohol use disorder according to DSM-5, i.e., the presence of at least 4 of the 11 criteria, or if significant physical alcohol withdrawal symptoms were reported anamnestically or observed by study physicians (CIWA at V3 or V4 > 6 points).
 - "Low" if there is only a mild alcohol use disorder according to DSM-5, i.e., the presence of no more than 3 of the 11 criteria, and physical withdrawal symptoms were neither reported anamnestically nor observed by physicians..

b) Answer to the question at time V4 as to whether patients want to reduce their alcohol consumption ("yes" or "no")

This stratification aims to ensure that the distribution of these two characteristics does not differ between the three treatment arms before the start of treatment.

It is hypothesized that acamprosate will have a more pronounced effect the more severe the addiction-related pathological changes in the reward system are. This aspect is captured by the composite factor "Severity of Addiction Characteristics" (criterion a).

Since the overwhelming majority of acamprosate studies in humans only included patients who wanted to reduce or stop their alcohol consumption, the clinical efficacy insights of acamprosate are limited to this group. On the other hand, it seems

inappropriate to make the desire for reduction a prerequisite for participation, as based on animal experiments and the observations of Mason et al. (2006), acamprosate reduces alcohol consumption even when there is no explicit desire for change, especially under the specific conditions of prior enforced abstinence.

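### The between-arm adverse-event table and its possible chi-square test run from V1 to V6, so they count events that occurred before any randomised drug

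*SAP*

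**What the plan says.** Section 4.3.2 defines the safety endpoint as "Occurrence of adverse events from visit V1 to V6", under the heading "Endpoints related to safety/tolerability during the treatment period". Section 6.5.3 repeats the window and applies it by arm: "The frequencies of adverse events in the treatment groups between V1 and V6 will be presented in cross-tabulations", adding that "a group comparison will be made using a chi-square test if applicable".

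The timing of randomised drug has to be pieced together from other sections:

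- Section 6.3 stratifies randomisation on addiction severity assessed up to V4, and on "Answer to the question at time V4 as to whether patients want to reduce their alcohol consumption". The stated aim is that "the distribution of these two characteristics does not differ between the three treatment arms before the start of treatment".
- Section 1.1 describes the primary contrast as "between Visit 2 (without medication) and Visit 5", so V2 is a visit off drug.
- Section 1.2 names the "alcohol self-administration visits V2 and V5", so alcohol is infused at V2.
- Section 2.1 treats the placebo lead-in and alcohol as separate from the randomised product when it defines the ITT population.
- Section 2.4 admits subjects to the Safety Analysis Set from the placebo lead-in onwards and assigns them to arms as treated.

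**The concern.** A comparison of adverse events between randomised arms should rest on events that the assigned drug could have influenced. Here the window opens at V1, while arms can be assigned only once the V4 information is available. Everything between V1 and the first randomised dose, including the V2 alcohol infusion and any placebo lead-in given before that dose, would be tabulated under arms that could not have caused it.

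The heading of section 4.3.2 suggests that treatment-period safety was intended, but the item beneath it starts at V1, so the heading does not narrow the window.

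What is at stake is sensitivity. Before randomised drug the arms are exchangeable, so earlier events do not push the comparison in either direction on average. If the table counts subjects with any event, a subject who already had an event before drug cannot register a new one, and the risk difference shrinks. If it counts events, the expected difference is unchanged but its variance grows. In both cases a real difference in tolerability is harder to see.

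A second point follows from section 2.4. A subject who took only the lead-in belongs to no randomised arm, yet under as-treated assignment could be placed in the placebo column.

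**Working it through.** The SAP states no event rate, arm size or power for this comparison, so there is no figure of its own to reproduce. The check has two parts.

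**1. Order of events (from the SAP)**

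| Point in time | What the SAP says | On randomised drug? |
|---|---|---|
| V1 | Adverse-event window opens (4.3.2, 6.5.3) | No |
| V2 | Alcohol self-infusion, without medication (1.1, 1.2) | No |
| V3, V4 | CIWA at V3 or V4 and the answer at V4 feed the strata (6.3) | Not before V4 |
| V5 | Alcohol self-infusion after study drug or placebo (1.1, 1.2) | Yes |
| V6 | Adverse-event window closes | Window ends |

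The SAP does not name the visit of the first randomised dose. But a subject cannot be allocated within strata that depend on V4 data before V4, so the stretch from V1 to V4 precedes randomised drug.

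**2. Illustration of the size (all rates assumed)**

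Assumptions: any-event rate on drug p = 20% in one arm and 45% in the other; pre-drug any-event rate q, equal in both arms; the two periods independent.

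*Subjects with at least one event.* Incidence over V1 to V6 is 1 − (1 − q)(1 − p), so the difference is (1 − q)(0.45 − 0.20). Subjects per arm for 80% power, two arms, two-sided 5%:

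n = [1.96·√(2·p̄(1 − p̄)) + 0.8416·√(p₁(1 − p₁) + p₂(1 − p₂))]² / (p₁ − p₂)², where p̄ is the mean of p₁ and p₂.

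| q | Incidence in the two arms | Difference | n per arm | Ratio to q = 0 |
|---|---|---|---|---|
| 0 | 20% vs 45% | 25 points | 53.9 → 54 | 1 |
| 5% | 24% vs 47.75% | 23.75 points | 62.8 → 63 | 1.17 |
| 20% | 36% vs 56% | 20 points | 96.3 → 97 | 1.79 |
| 40% | 52% vs 67% | 15 points | 166.9 → 167 | 3.10 |

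At an assumed fixed size of 30 per arm, power falls from 54% (q = 0) to 34% (q = 20%) and 22% (q = 40%).

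*Number of events.* With Poisson counts and the same inputs, the on-drug means are −ln(0.80) = 0.223 and −ln(0.55) = 0.598, a difference of 0.375 events per subject. The pre-drug mean is m = −ln(1 − q) = 0.051, 0.223 and 0.511 for q = 5%, 20% and 40%. It is added to both arms, so the difference stays 0.375. The standard error is multiplied by √[(0.223 + 0.598 + 2m)/(0.223 + 0.598)] = 1.06, 1.24 and 1.50.

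**The case against.** The strongest reply is that this matters little. The safety analysis is not confirmatory, the test is conditional, no power is claimed for it, and randomisation makes pre-drug events balanced in expectation. All of that is true, and it limits the weight of the point. It does not justify the window, because the cross-tabulation by arm is unconditional and loss of sensitivity is an unhelpful failing in a safety comparison.

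A second reply is that the tables might be split by visit or period, or that the protocol or a part of the SAP not available here defines treatment-emergent events. Either is possible. But the SAP states the V1 to V6 window twice, applies it explicitly to the arm comparison and asks for no split. A narrower definition elsewhere would conflict with this wording, which would still need correcting.

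Third, the wide window fits a safety set that starts at the lead-in and a study that infuses alcohol at V2. That supports recording and reporting events from V1. It does not support comparing arms over the whole period.

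Fourth, the illustrative figures establish nothing about this trial. That stands: the rates are assumed and the result runs from slight to large. If the table is by event type, each type has a pre-drug rate no higher than the any-event rate, so its risk difference shrinks less.

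**Conclusion.** The concern holds and should be fixed. As written, the comparison between arms includes the period from V1 to at least V4, when no randomised drug had been given. The conclusion rests on the inference that dosing cannot precede the V4 stratification data. That inference is firm, although the SAP does not state the first-dose visit.

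The consequence is dilution or added noise; there is no systematic bias and no effect on the primary analysis. Its size depends on the unknown pre-drug event rate: minor near 5%, substantial at 20% to 40%, under the assumed on-drug rates and independence of periods.

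**What to change.** In sections 4.3.2 and 6.5.3:

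- Keep recording adverse events from V1.
- Base the cross-tabulation by arm, and any chi-square test, on subjects with at least one dose of randomised product, as treated, counting events that start or worsen after the first such dose.
- State whether the table counts subjects or events.
- Report events before the first randomised dose, and all events of subjects who took only the placebo lead-in, in a separate table outside the three-arm comparison. The restriction to dosed subjects applies to the arm comparison; the Safety Analysis Set in section 2.4 can stay as it is for overall reporting.

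The cost is a change of SAP wording and one extra table, provided event onset dates and first-dose dates are recorded.

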6.5.4 Laboratory parameters

The relationship between activity and efficacy will be examined using correlation analyses and regression analyses. Group comparisons will be performed using ANOVA.

6.5.5 Pharmacokinetics

The relationship between body calcium reserves and efficacy will be is examined using correlation and regression analyses. Group comparisons will be conducted using ANOVA. The relationship between acamprosate levels in the acamprosate group and efficacy will be analyzed using correlation and regression analyses. Group comparisons will be conducted using ANOVA.

The changes in body calcium reserves will be compared between groups using repeated measures ANOVA.

6.6 SUBGROUP ANALYSES

Exploratory subgroup analyses will be conducted based on gender and the presence of alcohol dependence according to ICD-10 (yes/no) for the parameters mentioned in section 6.

6.7 INTERIM ANALYSES

No interim analyses are planned

7 SOFTWARE

The statistical analyses will be performed using the SPSS software and SAS System for Windows.
